## 2.1.2. Pooling Algorithm for Analysis Centers

All safety and efficacy analyses will be pooled over all centers. Some analyses will be shown by region and/or country.

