2.2. Hypothesis

This study is designed to test the primary hypothesis of VE in the PP population:

H0: VE(7-x months) ≤20% versus H1: VE(7-x months) >20%, with 24≤x≤30.

If the lower bound of the 95% CI for VE(7-x months) is >20% at the primary analysis, the corresponding H0 will be rejected.

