11.3. Sample Size Determination

This study is designed to test the primary hypothesis of VE in the PP population:

$H_0: VE(7-x \text{ months}) \leq 20\%$ versus the $H_1: VE(7-x \text{ months}) > 20\%$, with $24 \leq x \leq 30$ (See Section 11.5.1.1).

If the lower bound of the 95% CI for $VE(7-x \text{ months})$ is $>20\%$ at the primary analysis, the corresponding H_0 will be rejected.

The sample size calculations are based on the power of a 1-sided 0.025-level Wald test for comparing cumulative incidences of HIV-1 infection by the Month x visit ($24 \leq x \leq 30$) between randomized groups, in the presence of the sequential monitoring of VE. Power is computed based on simulating 10,000 efficacy trials using the R package seqDesign^{14,24} under the following assumptions:

[figure not shown]
- 10% annual dropout incidence in both groups;
- 5% of participants with at least one missed vaccination (excluded from PP population);
- VE 20% in the first 7 months after first vaccination;
- VE 65% from Month 7 onwards;
- 12-month uniform accrual with halved accrual during the first 3 months;
- Visits approximately every 3 months for HIV-1 diagnostic tests;
- 2% annual HIV-1 incidence in the placebo group;

Under these assumptions, a study of 3,800 participants (randomized 1,900:1,900 to vaccine:placebo) is expected to yield a total of 78 HIV-1 infections in the PP population between

the Month 7 and Month 30 visits, considered to be the TNI needed to achieve approximately 90% power for rejecting the primary H0, under an alternative VE of 65% and with a one-sided error rate of 2.5%.

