## 1.5. Randomization and Blinding

### *Procedures for Randomization and Stratification*

Participants will be randomly assigned to 1 of 2 treatment groups in a 1:1 ratio based on a computer-generated randomization schedule prepared before the study by or under the supervision of the sponsor. The randomization will be balanced by using permuted blocks and will be stratified by study site. Based on this randomization code, the study vaccine/placebo will be packaged and labeled for each participant.

Central randomization will be implemented in this study. The interactive web response system (IWRS) will assign a unique treatment code, which will dictate the treatment assignment and matching study vaccine/placebo vial for the participant. The requestor must use his or her own user identification and personal identification number when contacting the IWRS and will then give the relevant participant details to uniquely identify the participant.

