### 5.3.2. Analysis Methods

VE(7-x) is the target parameter for the primary analysis of overall VE. The primary analysis tests

the null hypothesis  $H_0: VE(7 - x) \leq 20\%$  versus

the alternative hypothesis  $H_1: VE(7 - x) > 20\%$

using a 1-sided 0.025  $\alpha$ -level Wald test of the difference of log cumulative hazard functions at month x for the vaccine group and the control group. See further details in Appendix 1. When the primary analysis is performed at month x (between 24 and 30), the failure times of participants with last HIV-1 negative test at or after the month x visit are right-censored at the right edge of the month x visit window. For participants with last HIV-1 negative test prior to the month x visit and without diagnosis of the HIV-1 infection primary endpoint at or before the month x visit, their failure times are right-censored at the date of the last HIV-negative test.

In addition, to assess potential time-effects of vaccine efficacy, the Nelson-Aalen method will be used to plot the estimated cumulative incidence rates over time for the vaccine and placebo groups. This method will be used to estimate cumulative vaccine efficacy over time, defined as above in 5.3.1, with the method of Parzen, Wei and Ying applied to construct pointwise and simultaneous  $(1 - 2\alpha) \times 100\%$  CIs. In addition, the fluctuations of the instantaneous VE will be visualized graphically (Gilbert, Wei, Kosorok, & Clemens, 2002).

Cox proportional hazards model will also be used for estimating VE(7-x months), measured by one minus the hazard ratio (vaccine versus placebo) and testing whether the VE(7-x months) is  $>$  or  $\leq 20\%$ . For the Cox proportional hazards model, the same censoring will be applied as for the cumulative incidence model used for the primary analysis.

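### Randomisation is stratified by site, but no efficacy analysis is planned to use the site strata, including the supportive Cox model

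*SAP*

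**What the plan says.** On allocation, SAP Section 1.5 states: "The randomization will be balanced by using permuted blocks and will be stratified by study site". Protocol Section 5 says the same, and site is the only stratification factor.

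On analysis, SAP Section 2.1.2 states: "All safety and efficacy analyses will be pooled over all centers". Its next sentence allows some results to be displayed by region or country.

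The primary analysis (SAP Sections 5.3.1 and 5.3.2, Appendix 1) is a two-group ratio of Nelson-Aalen estimates with a Wald test on the log scale. It has no site term.

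The Cox model is additional. In SAP Section 5.3.2 the sentence beginning "Cox proportional hazards model will also be used for estimating VE(7-x months" goes on to the hazard ratio and the 20% threshold, and the next sentence gives the censoring rule. Neither mentions strata or covariates. Protocol Section 11.5.1.2 places this model among the secondary and exploratory analyses. SAP Section 5.4.1 carries every method of Section 5.3.2 into the key secondary mITT-2 analysis.

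SAP Sections 2.2.4 and 5.4.2.3 list region and country as possible subgroups or covariates. Site is not listed, and no reason for leaving it out is given.

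**The concern.** When allocation is balanced within strata, the usual expectation is that at least one analysis conditions on those strata. If baseline hazards differ between sites, a Cox model that pools them estimates a hazard ratio pulled slightly towards one, and its test tends to be a little conservative.

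Site is plausibly prognostic here. The trial spans Europe, Latin America and the USA. PrEP is taken under site-specific plans, and the sponsor's own sizing argument (protocol Section 11.3) has PrEP use lowering incidence from 3% to 2% a year.

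At stake are a little efficiency in a supportive analysis, and a predictable question about whether the trial was analysed as randomised. The validity of the primary result is not at stake.

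**Working it through.** **1. The plan's own figure.** Inputs from protocol Section 11.3:
- 1,900 per group, 5% excluded from the PP population, 10% annual dropout, 2% annual placebo incidence.
- Effects: "VE 20% in the first 7 months after first vaccination" and "VE 65% from Month 7 onwards".
- Test: "The sample size calculations are based on the power of a 1-sided 0.025-level Wald test", against a null ratio of 0.80.

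Read the annual figures as rates and start from 1,900 × 0.95 = 1,805 per group.
- Placebo: 1,805 × exp(−0.12 × 7/12) × (0.02/0.12) × [1 − exp(−0.12 × 23/12)] = 57.6.
- Vaccine: 1,805 × exp(−0.116 × 7/12) × (0.007/0.107) × [1 − exp(−0.107 × 23/12)] = 20.5.
- Total: 78.1, against the stated 78.

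Power = Φ{ln(0.80/0.35)/√(1/57.6 + 1/20.5) − 1.96} = Φ(0.827/0.257 − 1.96) = 89.5%. The plan calls 78 "considered to be the TNI needed to achieve approximately 90% power for rejecting the primary H0", so both figures are reproduced. This calculation contains no site term.

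**2. Effect of using the site strata.** The simulation used the same inputs with site-stratified permuted blocks. Number of sites, block size (4) and between-site SD of log incidence are assumptions, because the documents give none of them. There were 4,000 runs per scenario for power and 6,000 for type I error, so the simulation error is about √(0.9 × 0.1/4,000) = 0.5 points and √(0.025 × 0.975/6,000) = 0.2 points. Each cell gives pooled Cox / site-stratified Cox, both tested against VE 20%.

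| Sites | SD | Power at VE 65% (%) | Difference | Median VE at true 65% (%) | One-sided type I error at VE 20% (%) |
|---|---|---|---|---|---|
| 25 | 0 | 92.57 / 92.45 | −0.12 | 65.4 / 65.4 | 2.37 / 2.52 |
| 25 | 0.7 | 92.13 / 92.55 | +0.42 | 64.8 / 65.1 | 2.20 / 2.40 |
| 25 | 1.2 | 89.92 / 91.40 | +1.48 | 64.3 / 65.2 | 1.77 / 2.17 |
| 50 | 0 | 92.13 / 92.15 | +0.02 | 65.3 / 65.3 | 2.55 / 2.57 |
| 50 | 0.7 | 91.25 / 91.43 | +0.18 | 64.7 / 65.0 | 2.22 / 2.40 |
| 50 | 1.2 | 89.68 / 91.17 | +1.49 | 64.0 / 65.0 | 2.02 / 2.63 |
| 80 | 0 | 91.37 / 91.33 | −0.04 | 65.2 / 65.2 | 2.07 / 2.12 |
| 80 | 0.7 | 91.15 / 91.80 | +0.65 | 64.8 / 65.1 | 2.20 / 2.48 |
| 80 | 1.2 | 88.42 / 90.52 | +2.10 | 64.1 / 65.3 | 1.82 / 2.48 |

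A separate paired simulation with 55 sites (3,000 runs) agreed. At SD 0, 0.7 and 1.2, power was 92.3/92.2%, 91.4/91.8% and 89.3/90.7%. At SD 1.2, median VE was 64.0% against 65.1% and type I error 1.8% against 2.5%.

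The pooled Nelson-Aalen test behaves like the pooled Cox test: power is 91–93% at SD 0 and 88–90% at SD 1.2, with type I error 1.7–2.5% throughout. Average standard errors of the two Cox fits agree to within 0.001.

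Read the table across rows, not down. Heterogeneity lowers the event count (about 77 at SD 0, 73 to 74 at SD 1.2). The simulation also ignores 3-monthly testing and DSMB monitoring, so absolute power is only indicative.

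**3. How strong is SD 1.2?** Sites one SD above and one SD below the centre would differ by a factor of exp(2.4) = 11; at SD 0.7 the factor is exp(1.4) = 4.1. The incidences cited in protocol Section 11.3 span 6.6/2.3 = 2.9-fold, but they come from separate earlier trials and do not measure spread between these sites. SD 1.2 is therefore a strong assumption.

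**The case against.** The best case for leaving the plan alone has five parts.
- **The harm is negligible.** At moderate heterogeneity the difference is within simulation error. In a further simulation with 55 sites in 8 countries (both assumed) and a country-level coefficient of variation of 1.0, power was 91.4% pooled, 91.9% stratified by country and 92.0% by site. Mean VE was 65.1% pooled, which is not below the true 65%.
- **Geography is partly covered.** Region and country are already foreseen as covariates, and country performs about as well as site.
- **The decision rule does not change.** Stratifying the Cox model leaves the primary Nelson-Aalen test as it is, so the trial's primary power gains nothing.
- **The SAP is past unblinding.** Its amendment history dates unblinding to 18 January 2023, after DSMB non-efficacy stopping, and versions 1.2 and 1.3 follow. Gains computed at VE 65% say little about a trial stopped for that reason.
- **'Unstratified' is an inference.** It rests on the silence of Section 5.3.2 together with the pooling rule.

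All of this stands, and it makes the point minor. It does not remove it: the only stratification factor is missing from every named analysis without a reason, and the covariates in Section 5.4.2.3 are optional. Sparse sites are not a barrier. With 78 events in 50 sites there would be about 1.6 per site. A site without events simply contributes nothing, and a site with events in one arm still contributes while both arms are at risk.

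**Conclusion.** The point holds as a minor improvement to a supportive analysis. On the plan as written, the site strata are not used in any efficacy analysis. Using them in the Cox model gains 0 to about 1.5 power points at VE 65% with 25 to 55 sites, and 2.1 points at 80 sites with strong heterogeneity. The upper figures need the strong-heterogeneity assumption. With no site differences, nothing measurable is lost.

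A reader might infer that pooling breaks the randomised comparison, biases it towards the vaccine or inflates alpha. The documents do not support that. Allocation is 1:1 within site, the pooled analysis compares the two randomised groups, and simulated type I error for the pooled Cox model was 1.8–2.6%, within simulation error of 2.5% at the top. Nor do the cited incidences of 2.3% to 6.6% establish that sites in this trial differ that much.

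**What to change.** In SAP Section 5.3.2, specify that the Cox model is stratified by site. Section 5.4.1 needs no edit, because it already imports the methods of Section 5.3.2. Amend Section 2.1.2 to read 'pooled over centers, with Cox models stratified by site'. Keep the pooled Nelson-Aalen Wald test as the primary analysis.

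Since the current SAP postdates unblinding, date the change in the amendment history, give the reason, and label the stratified fit as a supportive or sensitivity analysis.

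The cost is one phrase in each of the two sections, one strata statement in the program and a dated amendment entry.

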## 2.2. Analysis Sets

In the analyses the as-treated principle will be applied.

### 2.2.1. Full Analysis (FAS) Set

The full analysis set will include all randomized participants who receive at least one vaccine administration. This will be the primary population for the safety analysis.

### 2.2.2. Efficacy Analysis Set

#### 2.2.2.1. Per Protocol Population (PP)

The per protocol efficacy population will include all participants in the FAS population who have a negative HIV test 4 weeks post 3rd vaccination visit (i.e. at the Month 7 Visit) and who received all planned vaccinations at the first three vaccination visits within the respective visit windows. Participants with major protocol deviations linked to incorrect product administration will be excluded from the PP population. This will be the primary population for the efficacy analysis.

If participants miss their Month 7 Visit, and have a negative test in the first subsequent visit where an HIV-1 test is performed, these participants will remain part of the PP for the efficacy endpoints. If the HIV-1 test is positive at the first subsequent visit, participants are excluded from the PP for the efficacy endpoints. Handling rules of these participants for the immunogenicity correlates analysis will be described in a separate Correlates SAP.

#### 2.2.2.2. Modified Intent-to-Treat (mITT) population

The modified intent to treat efficacy population will include participants in the FAS who are HIV-1 uninfected at the date of the first vaccination. This will be a secondary analysis population for the efficacy analysis.

#### 2.2.2.3. Modified Intent-to-Treat-2 (mITT-2) Population

The mITT-2 will include participants in the FAS who have a negative HIV test 4 weeks post 3rd vaccination visit (ie, at the Month 7 Visit). This will be a secondary analysis population for the efficacy analysis.

If participants miss their Month 7 Visit, and have a negative test in the first subsequent visit where an HIV-1 test is performed, these participants will remain part of the mITT-2 for the efficacy endpoints. If the HIV-1 test is positive at the first subsequent visit, participants are excluded from the mITT-2 for the efficacy endpoints.

#### **2.2.2.4. Modified Intent-to-Treat-3 (mITT-3) Population**

The mITT-3 will include participants in the FAS who have a negative HIV test 4 weeks post 3rd vaccination visit (ie, at the Month 7 Visit) and who received all planned vaccinations at the first three vaccination visits regardless of the fact if the vaccinations were within the visit windows. Participants with major protocol deviations linked to incorrect product administration will be excluded from the mITT-3 population. This will be a secondary analysis population for the efficacy analysis.

If participants miss their Month 7 Visit, and have a negative test in the first subsequent visit where an HIV-1 test is performed, these participants will remain part of the mITT-3 for the efficacy endpoints. If the HIV-1 test is positive at the first subsequent visit, participants are excluded from the mITT-3 for the efficacy endpoints.

### **2.2.3. Immunogenicity Analysis Set**

#### **2.2.3.1. At risk Immunogenicity Cohort (IC-at risk)**

The IC-at risk will include participants in the FAS who are selected for measurement of immune response endpoints at the primary immunogenicity timepoints and who are HIV-1 uninfected 4 weeks after the 3rd vaccination visit (ie, at the Month 7 Visit).

#### **2.2.3.2. Others Analysis Sets**

The analysis sets described above can also be used for immunogenicity analysis purposes. The full immunogenicity analyses will be described in a separate Correlates SAP.

For the VISP analyses, a VISP analysis set is defined. Participants are in the VISP set if they received at least one active vaccination and did not become infected during the whole course of the trial.

### **2.2.4. Definition of Subgroups**

The following subgroups maybe be investigated for the most relevant efficacy outputs:

- Region (Europe, Latin America, USA)
- Age (18-20, 21-34, 35-44,  $\geq 45$ )
- Country
- P(r)EP use
- Baseline Ad26 status (when available)

### 3. SUBJECT INFORMATION

Participants information will be shown for the Full Analysis (FAS) set.

#### 3.1. Demographics and Baseline Characteristics

The following demographic and baseline characteristics will be summarized.

[Table 2](#) below presents a list of the demographic variables that will be summarized by vaccine regimen and overall for the FAS. Demographics will also be summarized by region and/or country using the FAS.

**Table 2: Demographic Variables**

Continuous Variables:	Summary Type
Age ([years])	Descriptive statistics (N, mean, standard deviation [SD], median and range [minimum and maximum]).
Weight (kg)	
Height (cm)	
Body Mass Index (BMI) (kg/m  )	
Categorical Variables	
Age ([18-20 years, 21-34 years, 35-44 years, and $\geq 45$ years])	
Sex at birth	
Gender at screening	
Country	
Race a	
Ethnicity	
BMI ([underweight <18.5 kg/m  , normal 18.5-<25 kg/m  , overweight 25-<30 kg/m  , obese $\geq 30$ kg/m  ])	
Baseline Risk Behavior, as identified by the attributes at Day 1	
Baseline STI testing results	
Other relevant factors	

aIf multiple race categories are indicated, the Race is recorded as 'Multiple'

#### 3.2. Disposition Information

The number and percentage of participants screened, participants in the FAS, participants vaccinated and not randomized, participants randomized and not vaccinated and discontinued participants (study discontinuation and vaccination discontinuation) with the reason of discontinuation will be tabulated per vaccine group and overall.

Also the number of participants and percentage per phase will be tabulated.

---

For the screen failures a tabulation will be made stating the frequency of all I/E criteria.

### **3.3. Treatment Compliance**

Adherence to vaccinations will be tabulated by vaccine regimen and overall, both for individual vaccinations as well as cumulatively over all vaccinations (received all vaccinations, missed 1 vaccination, missed 2 vaccinations, missed more than 2 vaccinations).

### **3.4. Social Impact Data**

Data from the Social Impact Questionnaire will be tabulated by vaccine regimen with emphasis on social impact events.

### **3.5. Sexual Activity Questionnaire**

Data from the sexual activity questionnaire will be summarized by vaccine regimen.

### **3.6. Use of PrEP**

Data from the questionnaire on the use of PrEP will be summarized by vaccine regimen.

### **3.7. Health Economics Aspects (HCRU)**

Health Care Resource Utilization will be summarized based on data collected through MAAEs and follow-up of HIV infections, and complemented by description of absenteeism.

### **3.8. Protocol Deviations and Quality Tolerance Limits (QTL)**

Major protocol deviations will be summarized by vaccine regimen.

In general, the following list of major protocol deviations categories may have the potential to impact participants' rights, safety or well-being, or the integrity and/or result of the clinical study:

- Developed withdrawal criteria but not withdrawn
- Entered but did not satisfy criteria
- Received a disallowed concomitant treatment
- Received wrong vaccination or incorrect dose

Participants with major protocol deviations will be identified prior to database lock and the participants with major protocol deviations will be summarized by category. Any Protocol deviations related to the COVID-19 pandemic will be labelled as COVID-19 related and will be shown in tables and listing.

Quality Tolerance Limit parameters and thresholds are defined and will be monitored in this study. QTL parameters will be summarized. More details are described in the Integrated Analytical Risk-Based Monitoring (iARBM) Plan.

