**AMENDMENT HISTORY**

Version 1.0	13 August 2019	Original version
Version 1.1	26 March 2021	Removal of interim analysis throughout document, References to CTP replaced by text from CTP (Section 1), Section 5.4.2 (Analysis Methods) removed and reference to 5.3.2 (Analysis Methods) added, added option of TAF monitoring (Section 3.5 Monitoring for the use of PrEP), References added
Version 1.2	31 August 2023	This version was created after unblinding of the study due to DSMB stopping rules for non-efficacy. Unblinding at study level took place on 18Jan2023.  Adverse events of special interest added in secondary safety endpoint (section 1.1). Quality Tolerance Limits added (Section 3.8). The mITT-3 analysis set has been added (Section 2.2). A VISp analysis set has been added (Section 2.2.3.2.). The censoring for the efficacy analysis is specified (Section 5.3.2). Other exploratory assays (e.g. BAMA and ICS ) might be considered (Section 6.3.1.1).
Version 1.3	4 March 2024	References added to reference list.

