### **Blinding**

The study participants, study-site personnel (except for those with primary responsibility for study vaccine preparation and dispensing), and investigator will be blinded to study vaccine allocation until the end of the study (see Section 10.1). The sponsor and its partners will be blinded to study vaccine allocation until the primary analysis, when the last participant has reached their Month x visit (with  $24 \leq x \leq 30$ ).

The pharmacist with primary responsibility for vaccine preparation (see CTP Section 14.3) will not be blinded to the study vaccine. In order to preserve blinding, he/she will place an overlay on the syringes. Administration of study vaccine to the participants will be performed by a blinded qualified healthcare provider from the study site.

The investigator will not be provided with randomization codes during the study. The codes will be maintained within the IWRS, which has the functionality to allow the investigator to break the blind for an individual participant.

Data that may potentially unblind the treatment assignment will be handled with special care to ensure that the integrity of the blind is maintained and the potential for bias is minimized. This can include making special provisions, such as segregating the data in question from view by the investigators, clinical team, or others as appropriate until the time of database lock and unblinding. Participants who discontinue vaccination early will be reminded that no HIV testing should be performed outside the study protocol to avoid unblinding.

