### **6. IMMUNOGENICITY ANALYSIS**

This section refers to the general analysis of immunogenicity and does not include details on the correlates analysis (separate SAP).

The analysis will be done on a subset of the complete set of participants who were randomized and vaccinated and for whom immunogenicity data are available, excluding participant samples with major protocol deviations expecting to impact the immunogenicity outcomes. Samples obtained after missed doses, incomplete doses or samples obtained after HIV infection will be excluded from the analysis.

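### The one judgement-based exclusion from the primary per-protocol set is tied to database lock, not to the unblinding of 18 January 2023, so the plan does not ensure that it was settled blind

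*SAP*

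**What the plan says.** - **The exclusion.** SAP 2.2.2.1 states: "Participants with major protocol deviations linked to incorrect product administration will be excluded from the PP population". Of the PP set it says: "This will be the primary population for the efficacy analysis". SAP 2.2.2.4 applies the same exclusion to mITT-3. The definitions of both sets in Protocol 11.2 contain no such exclusion.
- **The deadline.** SAP 3.8 says: "Participants with major protocol deviations will be identified prior to database lock". It lists four general categories of major deviation, one of which is a wrong vaccination or wrong dose. It sets no threshold for what counts as major.
- **The unblinding.** The SAP amendment history says of v1.2 (31 August 2023): "This version was created after unblinding of the study due to DSMB stopping rules for non-efficacy". It adds: "Unblinding at study level took place on 18Jan2023". The entry for v1.3 (4 March 2024) records only added references.
- **The planned sequence.** SAP 1.5 says that the sponsor and its partners "will be blinded to study vaccine allocation until the primary analysis". It also has potentially unblinding data kept apart "until the time of database lock and unblinding".
- **A set without the exclusion.** SAP 2.2.2.3 defines mITT-2 by FAS membership and Month 7 HIV status alone. SAP 5.4.1 makes VE from Month 7 to x in that set the key secondary analysis.

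**The concern.** A per-protocol set is chosen after randomisation, so its membership should be fixed without knowledge of arm or outcome. A deadline of database lock gives that protection only if lock comes before unblinding. The planned sequence named the two together and kept the sponsor blinded until the primary analysis, so the deadline would have served. The early stop broke that link, and the SAP versions written afterwards did not restore it.

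Under the present wording, a deviation could be raised, upgraded or downgraded after 18 January 2023 by someone who can see arm and HIV status, and the rule would still be met. At stake are the PP point estimate, its interval, and a reader's ability to tell whether the exclusions were made blind.

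**Working it through.** **1. Timing.** The only deadline is lock (SAP 3.8), and the lock date is not given. Unblinding was on 18 January 2023. SAP v1.2 is dated 225 days later and v1.3 411 days later; both still put the identification of deviations in the future tense. The rule therefore permits classification after unblinding. It does not show that any took place.

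**2. How much of PP membership is exposed.**
- First three vaccinations received: fixed rule.
- Given within the visit windows: fixed rule.
- Negative HIV test at Month 7: fixed rule, including the rule for a missed visit.
- Major deviation in product administration: judgement on whether it is major and whether it fits the description.

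Only the last is exposed. The other three categories in SAP 3.8 are to be summarised but are not stated as PP exclusions.

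**3. The plan's own figure.** SAP 1.4 expects 78 PP infections between Months 7 and 30. Inputs: 1,900 per arm, 5% excluded, dropout 10% a year, placebo incidence 2% a year, VE 20% to Month 7 and 65% after. Exponential rates are assumed. Formula, with a the incidence to Month 7, b the incidence after it, and d the dropout rate:

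infections = 1,900 × 0.95 × exp(−(a + d) × 7/12) × b/(b + d) × [1 − exp(−(b + d) × 23/12)]

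- Placebo (a = b = 0.020, d = 0.10): 57.6.
- Vaccine (a = 0.016, b = 0.007, d = 0.10): 20.5.
- Total: 78.1, which agrees with 78.

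**4. Leverage on the estimate.** Assume equal person-time, so that VE = 1 − v/p, with v vaccine and p placebo infections. The 95% limits are 1 − (v/p) × exp(±1.96 × √(1/v + 1/p)). Protocol Table 4 summarises the non-efficacy rule as lower bounds below 0% and upper bounds below 50%, for both VE(0-30) and VE(7-30). For simplicity the rule is applied here to a single count of infections.

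| Infections (v v p) | VE | 95% limits |
|---|---|---|
| 39 v 39 | 0% | −55.9% to 35.8% |
| 37 v 39 (two vaccine cases dropped) | 5.1% | −48.8% to 39.5% |

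The first row meets the Table 4 bounds. The splits that only just meet them, for assumed totals of 40, 60 and 78, are:

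| Split | VE | One vaccine case dropped | Two dropped | Drops needed for a lower bound above 20% |
|---|---|---|---|---|
| 20 v 20 | 0% | 5.0% | 10.0% | 14 |
| 28 v 32 | 12.5% | 15.6% | 18.8% | 15 |
| 35 v 43 | 18.6% | 20.9% | 23.3% | 15 |

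One or two reclassified cases move the estimate by about 2 to 10 points. Reaching success would take 14 or more, all in the vaccine arm.

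**5. Whether another analysis covers it.** mITT-2 keeps anyone whom the deviation rule would remove, but it also keeps those with missed or out-of-window doses. A difference between PP and mITT-2 therefore mixes three criteria.

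**The case against.** The strongest reply is that very little is exposed. Most PP criteria are mechanical. A wrong product or dose is largely a recorded fact, because Protocol 7 puts each administration in the CRF and Protocol 14.4 puts each vaccine given on an accountability form. The key secondary analysis in mITT-2 covers the same time window and is untouched by this judgement. The lock date is unknown, and a blinded review may be described in a document not supplied. All of this stands, and it limits the point. It does not close it, because the SAP itself offers only the lock deadline.

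Three stronger readings are tempting, and the documents support none of them.

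- A reader might infer that PP membership was decided unblinded. No text says so; the wording only allows it, and only for one criterion.
- A reader might infer that the PP exclusion was devised after unblinding, since Protocol 11.2 lacks it. The amendment history does not list it among the v1.2 changes. mITT-3 did enter the SAP in v1.2 and carries the same clause, but that does not date the clause for PP.
- A reader might infer that one reclassified case could turn the primary test. That needs a result near the success boundary. A trial stopped under a rule like that of Table 4 is far from it.

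A further fair objection concerns the remedy. Confirming a wrong vaccination means comparing assigned with given product, so full masking to arm is often impossible. Masking to HIV outcome is feasible.

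**Conclusion.** The point holds in limited form. The SAP's stated safeguard no longer ensures that the product-administration exclusion from PP and mITT-3 was applied without knowledge of arm and HIV status. The accept/reject decision is not realistically affected. The estimate could shift by a few points: 5.1 in the 39 v 39 example, and about 2 to 10 across the boundary splits. These sizes assume equal person-time, totals of 40 to 78 infections, and that the one or two participants removed are infected vaccine recipients. The documents give neither the number of such deviations nor any sign that one involved an infected participant. This is a cheap improvement in protection from bias and in transparency, not a demonstrated flaw in the result.

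**What to change.** - In SAP 3.8, replace the lock-based deadline with a rule that PP and mITT-3 deviation exclusions use the classification recorded on or before 18 January 2023. Refer to that rule in 2.2.2.1 and 2.2.2.4, which give no deadline of their own.
- Have any deviation added or reclassified after that date judged by staff masked to HIV outcome, and to arm where the type of deviation allows. List each with its date, reason, arm and case status.
- Report PP VE with and without the deviation-based exclusion, keeping the dose, window and Month 7 criteria in both.
- State the database lock date. If the exclusion list was already fixed before unblinding, say so; that sentence would largely settle the matter.

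The cost is SAP wording, one audit-trail extract and one extra run of the existing VE program. No new data are needed.
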